Study on the relationship between plasma MRD and cfDNA
HPV and the efficacy and prognosis of locally advanced
cervical cancer after concurrent chemoradiotherapy

Project Title: Relationship between plasma MRD and cfDNA HPV and efficacy
and prognosis after concurrent chemoradiotherapy for
locally advanced cervical cancer

Project leader/principal investigator: [name]

Department: Department of Oncology, Guizhou Provincial People's Hospital

Project undertaking unit: Guizhou Provincial People's Hospital

Project chair: Guizhou Provincial People's Hospital

Project Year: 2024/01 – 2026/12

Version number: V1.0

Version date: 2023-05-22

A. 、 Purpose of the study

1. Main objective: To detect the expression levels of MRD and plasma HPV before and after concurrent chemoradiotherapy for cervical cancer based on cfDNA liquid biopsy, and to evaluate the efficacy and recurrence risk of cervical cancer after concurrent chemoradiotherapy by the expression levels of MRD and plasma HPV
2. Secondary objectives: To facilitate clinical decision-making on whether to adjuvant chemotherapy, as well as the timing of adjuvant chemotherapy and the benefits of adjuvant chemotherapy through the expression levels of MRD and plasma HPV.

B. 、 Types of study design, principles and procedures

1. study design

This is a prospective, observational, single-center study

2. Study population and sample size considerations

Study population: Cervical cancer patients diagnosed with initial visit to Guizhou Provincial People's Hospital from November 2022 to November 2024 were collected.

Sample content estimation

There were about 30 cases in the experimental group, and the sample estimation was estimated by Power and Sample Size Program software, α 0.05, Power 0.8, δ and σ were obtained according to the literature review, m was 0.5.

2.1 Inclusion Criteria:

- (1) Age: ≥ 18 years old, ≤ 75 years old.
- (2) Pathological histologic confirmation of cervical cancer.
- (3) Imaging or PET/CT examination can be performed to understand the tumor

and complete all follow-up.

- (4) Measurable lesions before treatment.
- (5) Good physical condition: ECOG score 0-1 (or KPS score 70-100).
- (6) Estimated survival ≥ 6 months.

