2.4 Termination of study criteria

- (1) The patient's condition is aggravated.
- (2) Occurrence of serious adverse events.
- (3) Poor patient compliance.

3. Duration of the study

November 2022 to November 2024

4. Research interventions

This study was non-interventional.

5. Study steps and related checks

Before treatment: clear cervical pathology is required to confirm cervical cancer, complete imaging data, hematological data, laboratory test results

and comprehensive medical history.

Treatment period: Complete standard treatment of cervical cancer (concurrent chemoradiotherapy).

Follow-up period: Regular review at 4, 12 and 24 weeks after the end of treatment

6. Use and preservation of biological samples

Cervical tumor tissue was taken twice and made into wax blocks before treatment and during treatment (before the start of the first post-loading treatment); Clinically observe tumor retraction and monitor efficacy.

5ml of peripheral blood was drawn 5 times, respectively, before treatment, during treatment (before the start of the first after-loading treatment), 4 weeks, 12 weeks and 24 weeks after treatment, and serum and white blood cells were retained after treatment; Tested at Nanjing Shihe Medical Laboratory [name]

7. Evaluation indicators/study endpoints

The main endpoint indicators: the expression level and expression status of MRD and plasma HPV before, during, and 4, 12 and 24 weeks after treatment, the relationship between the expression level of MRD and plasma HPV expression status and the efficacy of concurrent chemoradiotherapy for cervical cancer, and the risk of recurrence after concurrent chemoradiotherapy for cervical cancer was predicted.

Secondary endpoints: decision on whether to give adjuvant chemotherapy after the end of concurrent chemoradiotherapy for cervical cancer by the expression level of MRD and the expression status of plasma HPV, as well as the timing of chemotherapy and the benefit of chemotherapy

8. Visiting arrangements and data collection during the study

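### Section B.6 keeps serum, whereas the title names plasma MRD and the objectives, endpoints and section B.8 name plasma HPV; the tested fraction is not stated

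*Protocol*

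**What the plan says.** Section B.6 (Use and preservation of biological samples) states that "5ml of peripheral blood was drawn 5 times": before treatment, during treatment, and at 4, 12 and 24 weeks afterwards. It continues that "serum and white blood cells were retained after treatment" and closes the instruction with "Tested at Nanjing Shihe Medical Laboratory". It does not mention plasma or say which fraction is tested.

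Elsewhere the study is framed in plasma:

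- The title reads "Study on the relationship between plasma MRD and cfDNA" HPV, so plasma is attached to MRD there.
- The main objective in section A describes the measurements as "based on cfDNA liquid biopsy" and names plasma HPV. The secondary objective names plasma HPV too.
- The primary endpoint in section B.7 is "the expression level and expression status of MRD and plasma HPV before, during, and 4, 12 and 24 weeks after treatment", together with its relationship to efficacy and recurrence.
- The secondary endpoint in B.7 concerns the adjuvant chemotherapy decision "by the expression level of MRD and the expression status of plasma HPV".
- Section B.8 refers to HPV in plasma and to plasma HPV tests at the three follow-up visits.

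The word serum appears in one other place, the albumin limit in the inclusion criteria, which has no bearing on this point.

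**The concern.** Serum and plasma are different specimens. Serum is the fluid left once blood has clotted, and plasma is the fluid separated from anticoagulated blood. The endpoint names one and the only handling instruction names the other.

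B.6 is the place where staff would look to find out what to separate and store, so the discrepancy is not confined to background text. Two things are at stake. The first is whether the measured quantity is the one the endpoint names. The second is whether levels from the five time points are on the same footing, since the primary endpoint sets out level and status at each of them. B.6 as worded secures neither.

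**Working it through.** No formula or stated figure is involved. The check sets the sections side by side.

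| Place in the protocol | Matrix named for MRD | Matrix named for HPV |
|---|---|---|
| Title | plasma | cfDNA, in the same phrase as plasma MRD |
| A, main objective | none (cfDNA liquid biopsy) | plasma |
| A, secondary objective | none | plasma |
| B.6, sample handling | serum and white cells kept; tested fraction not given | serum and white cells kept; tested fraction not given |
| B.7, primary endpoint | none | plasma |
| B.7, secondary endpoint | none | plasma |
| B.8, visits and data | none (peripheral blood) | plasma |

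Step 1. For HPV the contradiction is direct. Objectives, endpoints and B.8 all name plasma, and B.6 names serum.

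Step 2. For MRD it is less direct. The endpoint paragraphs attach the word plasma only to HPV, and for MRD it comes from the title.

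Step 3. Literal consequence. If serum is the cell-free fraction kept and tested, the HPV result is a serum result and does not match the endpoint as worded. It would still be a cell-free DNA result, but not the one named.

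Step 4. Timing. The words about retention after treatment can mean after the blood has been processed or after therapy has ended. Under the second meaning, the draws before and during treatment would have no retention instruction. The same sentence lists those two draws, which favours the first meaning. The ambiguity deserves correction but is not a separate defect.

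Step 5. Reach. 5 draws × 30 patients = 150 planned draws. The protocol says about 30 cases and allows withdrawal, so 150 is the number under full attendance. It counts the draws that the sentence covers and says nothing about how many are in the wrong matrix.

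Step 6. Dates. The version is dated 2023-05-22, while section B.8 starts inclusion on 1 November 2022. On these dates some blood may have been drawn before this text existed, so editing the sentence alone would not establish what was collected.

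**The case against.** The strongest reply is that serum is a slip for plasma. B.6 keeps a fluid fraction together with white cells, a pairing that ordinarily comes from anticoagulated blood, where the fluid is plasma. The wording elsewhere is consistently plasma, and the English is visibly a rough translation in other places. This is plausible and I accept it as a live possibility. It makes the correction easy, but it does not make the sentence right, and the document alone cannot settle which was meant.

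A second reply is that B.6 says what is retained, not what is tested, and does not forbid separating plasma. Section B.8 directs peripheral blood to MRD testing without limiting it to serum. This also stands. A reader might infer from B.6 that no specimen capable of giving the endpoint would remain, or that none of the 150 draws would be plasma. The text supports neither inference.

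A reader might also infer lost sensitivity, false negatives, or a mixture of serum and plasma across visits. The protocol describes no mixing and gives no assay figures. Arguments about extra background DNA from clotting come from outside the document, and I do not rely on them.

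Finally, the absence of tube type and anticoagulant could be called routine detail that belongs in a laboratory manual. I agree and do not raise it. The point is that the detail which is given conflicts with the endpoint.

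**Conclusion.** The point holds in limited form. The only blood-handling instruction names serum where the HPV endpoint, the objectives and section B.8 name plasma and the title names plasma MRD, and it leaves the tested fraction unstated. Read literally, it yields a serum HPV result for an endpoint defined in plasma. That is wrong as written and should be corrected.

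The size of any effect on results is unknown and cannot be derived from the protocol. The conclusion rests on two things: that B.6 is the instruction staff would follow, and that serum and plasma are distinct specimens whose levels should not be assumed interchangeable. It does not depend on serum having actually been collected. If the records show plasma throughout, what remains is a wording error with no consequence for the data.

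**What to change.** First, confirm from laboratory records which fraction was collected and tested at each draw, including any draws made before the version date.

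Then correct B.6 to say that plasma and white blood cells are separated and retained at each of the five draws, that plasma is the fraction tested for MRD and HPV, and that the same matrix is used at all time points. This wording also removes the ambiguity about retention after treatment.

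If any serum was tested, flag those samples and do not pool their levels with plasma levels. They can be reported separately or in a sensitivity analysis, so they need not be discarded.

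The cost is one corrected sentence and a records check, with no added procedure for patients. The one downside is that any serum-based levels would be reported apart from the main comparison, which in a study of about 30 patients could thin the data at the affected time points.

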From November 01, 2022 to November 31, 2024, 30 patients with newly treated cervical cancer admitted to Guizhou Provincial People's Hospital were included, 30 cervical cancer tissue samples were collected before treatment and during treatment (before the start of the first afterload), and 5ml of peripheral blood of cervical cancer patients was collected before, during treatment (before the start of the first afterload), and 4 weeks, 12 weeks and 24 weeks after the end of treatment to detect MRD expression levels. The relationship between the expression level of MRD and the expression status of HPV in plasma and the efficacy of cervical cancer treatment was analyzed.

Thirty cases of cervical cancer were treated with concurrent chemoradiotherapy, and the efficacy was evaluated 4 weeks after the end of chemoradiotherapy, and the value of MRD expression level and plasma HPV expression status for clinically guided adjuvant chemotherapy and adjuvant chemotherapy time node and clinical benefit were evaluated.

MRD and plasma HPV tests were performed 4 weeks, 12 weeks and 24 weeks after the end of concurrent chemoradiotherapy in 30 cases of cervical cancer to understand the risk of recurrence and predict prognosis. The expression level of MRD and the expression status of HPV in plasma and the clinical value of imaging results in predicting recurrence risk were compared.

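### The main endpoint names no single marker, time point and outcome, so the α 0.05 and power 0.8 in the sample-size statement belong to no identifiable primary comparison

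*Protocol*

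**What the plan says.** Section B.7 of the protocol sets the main endpoint in one sentence, which opens with "The main endpoint indicators: the expression level and expression status of MRD and plasma HPV". In full, its first limb is "the expression level and expression status of MRD and plasma HPV before, during, and 4, 12 and 24 weeks after treatment". The sentence then adds the relation of MRD level and plasma HPV status to the response to chemoradiotherapy, and finally the prediction of recurrence. All of this has the rank of main endpoint, and no marker, form of measurement, time point or outcome is put first. The main objective in section A has the same breadth: both markers, for both efficacy and recurrence risk.

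Section B.8 does not narrow this. It dates the efficacy assessment to week 4 after chemoradiotherapy and links recurrence to the samples at weeks 4, 12 and 24. It then adds a further question, in which the markers and "the clinical value of imaging results in predicting recurrence risk were compared".

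Section B.2 holds the only planning statement: "There were about 30 cases in the experimental group", with "α 0.05, Power 0.8, δ and σ were obtained according to the literature review, m was 0.5". It names no variable, time point or outcome. Section B.1 states the design: "This is a prospective, observational, single-center study".

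**The concern.** A sample-size calculation with one α, one power, one δ and one σ describes one comparison. The main endpoint is a set of many, and the protocol does not say which of them the calculation was made for. A reader of the results could not tell which association had been planned at 80% power and which had merely turned out to be the most striking.

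The choice of primary endpoint, and of the comparison that justifies the sample size, belongs in the protocol. Here it has not been left open for a later document: it has been fixed, as an unranked bundle. The consequence is practical. The secondary endpoint concerns using these markers to decide on adjuvant chemotherapy, so a chance association in 30 patients, presented as the main result, could carry weight beyond what the design supports.

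**Working it through.** **1. The plan's own figure.** The sample size of about 30 cannot be reproduced, because B.2 gives no value for δ or σ and does not define m. Solving for the effect instead, with two-sided α 0.05 and power 0.8 (normal approximation; sidedness is not stated, so two-sided is an assumption):

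δ/σ = (1.960 + 0.842) × √(1/n₁ + 1/n₂)

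| Assumed layout | Implied δ/σ |
|---|---|
| 30 + 15 (m read as control-to-experimental ratio) | 0.89 |
| 30 + 30 | 0.72 |
| 20 + 10 (30 in total) | 1.09 |
| 30, paired or one-sample: 2.802/√30 | 0.51 |

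The implied effect varies about twofold with the layout assumed, and nothing in the text selects a layout. Working back from the number 30 does not reveal the intended comparison.

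**2. How many comparisons the main endpoint contains.** The inputs are two markers (B.7), five blood draws (B.6 and B.7) and two outcomes, efficacy and recurrence (B.7).

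- *Narrowest reading, using the timing in B.8.* Efficacy is assessed at week 4, so only the draws before treatment, during treatment and at week 4 can inform it: 2 × 3 = 6. Recurrence is tied to weeks 4, 12 and 24: 2 × 3 = 6. Total 12.
- *Relationship clause of B.7 at all five times.* MRD by level and HPV by status give two marker variables: 2 × 5 × 2 = 20.
- *Full crossing.* Level and status for both markers: 2 × 2 × 5 × 2 = 40.

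The comparison with imaging in B.8 is a separate question and is in none of these counts.

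**3. What an unranked bundle would allow.** Suppose there is no true association, each comparison is tested at 0.05, and any one significant result counts as a positive main finding. These are assumptions; the protocol states no such rule. For k independent tests the chance of at least one false positive is 1 − 0.95ᵏ. For dependence, the test statistics were simulated as equicorrelated normal variables (200,000 draws, two-sided). The correlations are assumed.

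| k | Independent | Correlation 0.5 | Correlation 0.9 | Expected false positives (0.05k) |
|---|---|---|---|---|
| 12 | 46.0% | 31.9% | 13.5% | 0.6 |
| 20 | 64.2% | 41.8% | 15.5% | 1.0 |
| 40 | 87.2% | 57.1% | 18.4% | 2.0 |

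The expected number of false positives does not depend on the correlation. The smallest probability in the table, 13.5%, is 2.7 times 5%.

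**The case against.** The strongest reply is that the protocol makes no error-rate claim that could be broken. α appears once, as an input to sample-size software, and there is no stated test, success rule or family-wise rate. The study is observational, and the statistical analysis plan, where handling of multiple tests normally sits, is not at hand. This stands against two inferences that a reader might draw. One is that the study fails to hold an error rate it promises; it promises none. The other is that the lack of a multiplicity method is itself a defect; it may be in the analysis plan and cannot be held against the protocol.

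It is also fair to say that the larger counts overreach. B.7 relates MRD by level and HPV by status to outcome, so the 40 needs a crossing that the text does not ask for. Samples taken after week 4 cannot predict a week-4 response, which brings the count down to 12. Part of the endpoint, the course of the markers over time, is descriptive. Repeated measurements in the same 30 patients will be correlated, so the independence column is a ceiling for positively correlated tests such as these, not the study's actual rate.

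A reader might also want to state the power left after a Bonferroni correction. The documents do not support such a figure: it needs δ, σ and a group layout, and none is given.

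What the reply does not answer is the central point. The protocol calls itself observational but not exploratory, it quotes α and power, and it does not say for which comparison.

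**Conclusion.** The point holds in a limited form. The main endpoint gives equal rank to two markers, five time points and two outcomes, and the α 0.05 and power 0.8 in B.2 attach to no identifiable member of that set. This is a badly fixed endpoint in the protocol, not a gap that an analysis plan would ordinarily fill.

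On the narrowest count, and over the assumed correlations from 0.9 down to independence, the chance of at least one false-positive main result is 13.5% to 46%. The higher figures need the wider counts. All of them depend on the assumptions that each comparison is tested at 0.05, that any one success suffices, and that there is no true association. They show what the present wording would permit, not what the study will do. The matter should be corrected, and the correction is small.

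**What to change.** Either of two changes would settle it.

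1. **Name one primary comparison.** In B.7, specify one marker, its form (level or status), one time point and one outcome. In B.2, state that α 0.05 and power 0.8 refer to that comparison and give the δ, σ and group layout used. If those inputs do not support power 0.8 with about 30 patients, restate the power. Label every other combination of marker, time and outcome exploratory, reported with confidence intervals and without a claim of significance.
2. **Declare the study exploratory.** State that the whole study is exploratory and estimates associations, and remove the power claim from B.2.

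Both are changes of wording and need no extra patients, samples or assays. The price of the first is that the remaining associations can no longer be presented as main confirmatory results. The price of the second is that none of them can.

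### The benefit and timing of adjuvant chemotherapy are secondary endpoints, but a single non-interventional cohort of 30 cannot identify either; the endpoint should be descriptive

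*Protocol*

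**What the plan says.** Adjuvant chemotherapy appears in three places in the protocol.

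- **A.2 (secondary objectives):** the markers are to help decide whether to give it, "as well as the timing of adjuvant chemotherapy and the benefits of adjuvant chemotherapy".
- **B.7 (secondary endpoints):** the decision by MRD level and plasma HPV status, "as well as the timing of chemotherapy and the benefit of chemotherapy".
- **B.8:** the value of the markers for guiding adjuvant chemotherapy, its time point and its clinical benefit is to be evaluated in the 30 patients.

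The design is fixed elsewhere.

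- **B.1:** "This is a prospective, observational, single-center study".
- **B.4:** "This study was non-interventional".
- **B.5, treatment:** "Complete standard treatment of cervical cancer (concurrent chemoradiotherapy"). No other treatment is set.
- **B.5, follow-up:** "Regular review at 4, 12 and 24 weeks after the end of treatment". No later review is scheduled.
- **Dates:** the cover has "Project Year: 2024/01 – 2026/12"; B.3 has "November 2022 to November 2024".

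No group with or without adjuvant chemotherapy is defined. The sample-size note in B.2 mentions an experimental group and m = 0.5, but no control group is described.

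**The concern.** Whether chemotherapy helps, and when it is best started, are questions about a treatment effect. They need patients who are comparable apart from receiving it, or apart from when they start. This design does not provide them.

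- **If MRD/HPV status decides treatment,** marker and treatment coincide, and their effects cannot be separated.
- **If it does not,** a treated-untreated contrast can be computed. Clinicians will have chosen whom to treat by perceived risk, so it is confounded by indication, and it rests on very few patients.
- **For timing,** a patient can start late only by staying recurrence-free until then, which favours late starting. Little scheduled follow-up remains after the later marker results.

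Followed as written, the endpoint invites a conclusion on giving, withholding or delaying chemotherapy that the data cannot support.

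**Working it through.** **The plan's own figure.** The 30 in B.2 cannot be reproduced: α = 0.05, power = 0.8 and m = 0.5 are given, but δ and σ have no values and m is not defined. Nothing there refers to adjuvant chemotherapy, and the point does not depend on it.

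**From the document: scheduled follow-up after each marker result.** Week 4: 24 − 4 = 20 weeks. Week 12: 24 − 12 = 12 weeks. Week 24: 24 − 24 = 0 weeks.

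Everything below uses assumed rates, because the protocol gives no recurrence risk, chemotherapy uptake or effect.

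**1. Power, ignoring confounding.** Assume an even 15 v 15 split and two-sided α = 0.05. With untreated risk p and hazard ratio HR, the treated risk is q = 1 − (1 − p)^HR.

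| p | HR | q | Fisher exact | Normal approx. | n per group, 80% power |
|---|---|---|---|---|---|
| 0.20 | 0.5 | 0.106 | 0.038 | 0.105 | 227 |
| 0.20 | 0.7 | 0.145 | 0.023 | 0.059 | 729 |
| 0.40 | 0.5 | 0.225 | 0.083 | 0.172 | 110 |
| 0.40 | 0.7 | 0.301 | 0.034 | 0.081 | 361 |
| 0.60 | 0.5 | 0.368 | 0.129 | 0.240 | 72 |
| 0.60 | 0.7 | 0.473 | 0.044 | 0.101 | 243 |

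If chemotherapy prevented every recurrence, Fisher power would be 16% at p = 0.20, 48% at 0.30, 78% at 0.40 and 99% at 0.60.

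**2. Confounding by indication.** Assume half the patients are high-risk (recurrence hi = 0.4-0.6) and half low-risk (lo = 0.2-0.3). Chemotherapy goes to a share t = 0.6-0.8 of the high-risk and 1 − t of the low-risk. With f(r) = 1 − (1 − r)^HR:

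- treated risk = t·f(hi) + (1 − t)·f(lo)
- untreated risk = (1 − t)·hi + t·lo

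Worked case, no effect (HR 1), hi = 0.6, lo = 0.2, t = 0.8: treated 0.8 × 0.6 + 0.2 × 0.2 = 0.52; untreated 0.2 × 0.6 + 0.8 × 0.2 = 0.28. An inert treatment looks 24 points harmful.

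The same case with HR 0.7: treated 0.8 × 0.473 + 0.2 × 0.145 = 0.408 against 0.28, an apparent harm of 13 points.

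Untreated minus treated risk over the whole range:

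| HR | Apparent difference | True difference |
|---|---|---|
| 1.0 | −0.24 to −0.02 | 0 |
| 0.7 | −0.128 to 0.071 | 0.077 to 0.103 |
| 0.5 | −0.035 to 0.139 | 0.135 to 0.185 |

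This bias does not shrink with more patients.

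**3. Late start.** Assume no effect, a constant hazard and 24-week recurrence R. Count recurrences from the start of chemotherapy to week 24, without correction. Week-4 starters show 1 − (1 − R)^(20/24); week-12 starters show 1 − (1 − R)^(12/24).

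| R | Week-4 start | Week-12 start | False advantage of later start |
|---|---|---|---|
| 0.10 | 0.084 | 0.051 | 3 points |
| 0.20 | 0.170 | 0.106 | 6 points |
| 0.40 | 0.347 | 0.225 | 12 points |

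**The case against.** - **Reading.** The protocol never says causal, best or optimal. A.2 and B.8 can be read as asking how useful the marker is, and B.7 also ties the decision to the markers. This stands as a fair reading and limits the point to benefit and best timing. It does not remove it: a marker's value for predicting benefit from chemotherapy also needs a treated-untreated contrast, and B.7 names the benefit of chemotherapy as an endpoint.
- **The SAP.** Covariate adjustment, landmarking and the choice of contrast usually belong there, and landmarking or person-time would address the late-start bias in step 3. That step therefore shows a risk, not an analysis the protocol proposes. No SAP can create unconfounded assignment, and 30 patients with few events cannot carry credible adjustment.
- **Assumed sizes.** Only the 20, 12 and 0 weeks come from the document. Power is also adequate in the extreme case (99% if untreated recurrence is 60% and chemotherapy prevents all of it). Both are true; neither affects the confounding argument.
- **Longer follow-up.** The cover's period to 2026/12 makes later recurrence data possible. B.5 schedules no review after week 24, and longer follow-up would not remove confounding.
- **Consequence.** The endpoint is secondary, no chemotherapy is assigned, and the primary aim is untouched. That limits the severity of the point.

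**Conclusion.** The concern holds. The protocol names a secondary endpoint that its own design cannot deliver. This follows from the document alone: treatment is not assigned, there is one cohort of 30, and no comparator is defined.

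The size depends on the assumed ranges. Within them, power for realistic effects is 2-13% by Fisher's exact test (6-24% by the normal approximation), and with HR 0.7 even the direction of the apparent effect is unreliable. Timing can be described, but the best timing cannot be identified. The change should be made, though it concerns a secondary claim only.

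**What to change.** In A.2, B.7 and B.8, reword the secondary aim along these lines: *describe adjuvant chemotherapy use, time from the end of chemoradiotherapy to its start, and recurrence, by post-treatment MRD/HPV status*. Report counts with exact intervals, and drop any conclusion on the benefit of chemotherapy or its optimal timing. Optionally, state whether marker results reach the treating team, since that determines whether marker and treatment coincide.

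The cost is wording in three places, with no added patients, visits or assays. The sponsor gives up a claim the design cannot support. The descriptive intervals will be wide: 5 recurrences in 10 patients gives an exact (Clopper-Pearson) 95% interval of 19-81%.
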